The objective of this proposal is to adapt PPE training guidelines issued by the World Health Organization (WHO)³⁶ and the U.S. Occupational Safety and Health Administration (OSHA)³³ for use by healers and to fill the current evidence-to-practice gap by comparing effectiveness of two practical strategies for implementing evidence-based PPE guidelines.

Our proposal compares two implementation strategies to increase PPE use and proper disposal during procedures and decrease the number of risky injections performed (de-implementation of traditional injections): (1) Health care worker (HCW)-led education on blood exposure risk and PPE use through a week-long training, followed by three educational outreach visits at the healer's place of practice vs. (2) "Early adopter" healer³⁷⁻⁴⁰ and HCW co-led training followed by three educational outreach visits. We hypothesize that "early adopter" healer messaging and delivery will have greater impact given their membership within the healer community.

Aim 1. Gather information about how healers and health care workers are learning about PPE use to develop an acceptable and appropriate PPE training program.

Aim 2: Compare fidelity to delivery of PPE training between the HCW-only and the healer plus HCW teams.

We will compare training fidelity of the two teams via three constructs: (1) content, (2) coverage, and (3) duration^{41,42} to determine if there is a difference in fidelity between the two types of teams.

Hypothesis 1: Training fidelity will be greater among healer + HCW teams, as they will have greater motivation to comprehensively deliver education and skill building sessions to healers.

Aim 3: Compare the effects of the two implementation strategies on healer exposure to patient blood.

We will enroll traditional healers into each PPE strategy using a stratified random sampling. Healers will use containers to collect all used sharps and used gloves over a six-month period and complete a low literacy data collection form to document glove use to identify gaps in PPE use.

Hypothesis 1: Healers who are trained by the healer + HCW team will have a higher proportion of glove use during injections than those in the HCW-only trainer arm.

4. Study Population

Population

Traditional healers and biomedical practitioners (including clinicians and nurses) providing patient care in the Bushbuckridge area.

Inclusion Criteria

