Aim 3: From preliminary data collected from healers in Agincourt in 2019, the median proportion of glove use during vaccinations was 0.44, mean 0.39, and standard deviation (SD) 0.39. Our sample size is calculated based on a two-sample t-test and incorporates these preliminary data. Assuming the SD=0.39, then we anticipate needing 61 healers per arm (total of 122) to have 80% power to detect at the ($\alpha=0.05$ -level) a difference of 0.2 in the proportion glove use between the HCW-only and the healer + HCW teams (e.g., 0.4 vs. 0.2). Included below is the variability in power given different deltas (differences in the mean proportion of blood exposure between the two arms) (Table 1). Note, that these power calculations are approximate as primary analyses will be performed using negative binomial regression. Power calculations using negative binomial regression would require assuming a distribution of the offset (number of procedures performed per healer), which substantially complicate the calculations. Therefore, we present power calculations based on two-sample t-tests, which should be fairly similar.

Table 1 Sample Size and Power

N	Δ	SD	α	P
61	0.17	0.39	0.05	66.57
61	0.18	0.39	0.05	71.52
61	0.19	0.39	0.05	76.08
61	0.20	0.39	0.05	80.22
61	0.21	0.39	0.05	83.89

61	0.22	0.39	0.05	87.08
61	0.23	0.39	0.05	89.81
61	0.24	0.39	0.05	92.09
61	0.25	0.39	0.05	93.96

N: number of healers per arm

Δ: Difference to detect (delta)

SD: Standard deviation

α: Significance level (alpha)

P: Power, %

Randomization strategy

To avoid concerns that, despite randomization, one intervention arm of healers will substantially differ from the other, we will conduct stratified randomization. Specifically, we will stratify based on healer sex and the number of patients seen in a given month (dichotomized into high/low based on the estimated median number of patients seen in the past month). This will result in 4 strata. At the time of randomization, each healer will be put in a strata and equal numbers of healers in each strata will be randomized to the two intervention arms.

5. Methods

Measurement of Results

Aim 1: We will use qualitative measures to understand the best strategies to delivery PPE training to traditional healers in Bushbuckridge.

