Analysis plan for coverage: We will calculate the percentage of sessions completed as the actual number of sessions completed for a participant divided by the total number of planned sessions. The percentage of sessions completed between the two intervention arms will be compared using mixed effects Poisson regression with the number of planned sessions (in most cases 3) as an offset. 95% confidence intervals will be constructed. The models will include random effects for the trainers. Covariates will include patient volume, sex, and baseline age. Missing data and LTFU will be handled as described above.

Aim 3: The analysis will follow intent-to-treat protocol. Our primary outcome is the proportion of a healer's procedures that were conducted using latex gloves (numerator = number of procedures with blood exposure, denominator = number of procedures). We will compare the blood exposure proportions between the two study arms using a negative binomial regression model. In the negative binomial regression, the outcome will be the number of times gloves were used and the number of procedures performed by the healer (number of razor blades) will be included as an offset. Such an analysis is appropriate because it properly accounts for heterogeneity between healers in the number of procedures performed, and the resulting estimates from the model can be interpreted as relative proportions (proportion of procedures with blood exposure in Arm 1 vs. proportion of procedures with blood exposure in Arm 2). In addition to our primary intervention

exposure variable, we will include healer sex and baseline age as covariates in our model. Sensitivity analyses will compare blood exposure proportions between the two intervention arms using a two-sample t-test; a Wilcoxon rank sum test will be fit as needed to avoid normality assumptions.

Based on prior experience working with healers, we anticipate very low rates of loss to follow-up (LTFU). Healers who are LTFU will be censored at the time of their last recorded data collection, and inverse-probability of censoring weights based on healer characteristics randomization will be used, if necessary, to account for differences between healers who are LTFU and those who remain in the study. Missing data will be imputed using chained equations and 20 imputation replications.

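### The Aim 3 primary analysis models glove use but defines and interprets the result as blood exposure, which would reverse the stated effect if exposure means no gloves

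*Combined protocol and SAP*

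**What the plan says.** Section 7, Data Analysis, Aim 3 uses two outcomes as if they were one.

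- **Definition.** The primary outcome is the proportion of procedures "conducted using latex gloves (numerator = number of procedures with blood exposure, denominator = number of procedures". The description is glove use; the numerator is blood exposure.
- **Contrast.** "We will compare the blood exposure proportions between the two study arms using a negative binomial regression model".
- **Model.** In that regression "the outcome will be the number of times gloves were used", with the number of razor blades as offset.
- **Interpretation.** The estimates are to be read as "proportion of procedures with blood exposure in Arm 1 vs. proportion of procedures with blood exposure in Arm 2".
- **Sensitivity.** "Sensitivity analyses will compare blood exposure proportions between the two intervention arms".

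The rest of the protocol is also mixed. In Section 2 the Aim 3 title is "Compare the effects of the two implementation strategies on healer exposure to patient blood", but its hypothesis is "Healers who are trained by the healer + HCW team will have a higher proportion of glove use during injections" than in the HCW-only arm. Section 5, Measurement of Results, takes glove pairs over razor blades. Section 4 sizes the trial on a difference of 0.2 "in the proportion glove use between the HCW-only and the healer + HCW teams (e.g., 0.4 vs. 0.2"), and then describes the Table 1 delta as a difference in blood exposure.

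**The concern.** More glove use is favourable; more blood exposure is not. One estimate cannot be labelled as both without its direction becoming unclear. A model of glove counts with a log razor-blade offset estimates a ratio of glove-use proportions. It does not estimate the ratio the plan says it does.

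The affected text is the definition and reading of the primary result. An analyst who fits the model as specified and reports it as instructed would present a benefit as a harm, or a harm as a benefit. An analyst who takes the stated numerator literally would fit a different count and get a different primary ratio. The result would depend on which sentence was followed.

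Two further gaps make this harder to settle from the text. Blood exposure has no definition, and the interpretation sentence refers to Arm 1 and Arm 2 without saying which team is which. Section 2 numbers the two strategies, but nothing ties those numbers to the arms in the model.

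**Working it through.** **Step 1: the plan's own power figure.** Inputs from Section 4, Aim 3: 61 healers per arm, SD 0.39, alpha 0.05 (taken as two-sided), difference 0.20. For a two-sample t-test with 120 degrees of freedom, the noncentrality is 0.20 / (0.39 × √(2/61)) = 0.20 / 0.0706 = 2.83, which gives power 80.22%. Table 1 prints 80.22. All nine rows, from 66.57 at 0.17 to 93.96 at 0.25, reproduce to two decimals.

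Replacing each proportion p by 1 − p leaves the SD and the absolute difference unchanged. The power figures therefore stand under either label.

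**Step 2: the two ratios.** Let pC be glove use in the HCW-only arm and pI glove use in the healer + HCW arm, with one common proportion per arm. Assume exposure = 1 − glove use.

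- Ratio the model fits: pI / pC
- Ratio the text says it is: (1 − pI) / (1 − pC)

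If pI > pC, then 1 − pI < 1 − pC, so the first ratio is above 1 and the second below 1. If pI < pC, the reverse holds. The two always fall on opposite sides of 1 unless there is no effect. Swapping the arms replaces both by their reciprocals and leaves the contradiction in place.

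**Step 3: the Section 4 example.** The pair 0.4 and 0.2 can be read in three ways, because the text calls it glove use, lists HCW-only first, and labels the Table 1 delta as exposure.

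| Reading of the example | pC | pI | Fitted ratio | Exposure ratio | 1 / fitted |
|---|---|---|---|---|---|
| (a) Glove use, hypothesised direction | 0.2 | 0.4 | 0.4/0.2 = 2.00 | 0.6/0.8 = 0.75 | 0.50 |
| (b) Glove use, order as printed | 0.4 | 0.2 | 0.2/0.4 = 0.50 | 0.8/0.6 = 1.33 | 2.00 |
| (c) Exposure, order as printed | 0.6 | 0.8 | 0.8/0.6 = 1.33 | 0.2/0.4 = 0.50 | 0.75 |

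In (a) a 25% fall in exposure would be read as a doubling. In (b) a 33% rise would be read as a halving. In (c) a halving would be read as a 33% rise. Reading (b) also contradicts the Section 2 hypothesis, whereas (c) agrees with it, so the example does not show which outcome was meant.

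**Step 4: whether inverting the estimate would repair it.** Setting pC/pI = (1 − pI)/(1 − pC) gives (pC − pI)(1 − pC − pI) = 0. With a real effect this requires pC + pI = 1. None of the three readings meets that condition, so inversion restores the direction but not the size.

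**Step 5: check with the negative binomial model.** An illustrative simulation of 300 trials used 61 healers per arm, beta-distributed glove proportions with means 0.4 and 0.2, and an assumed average of about 31 procedures per healer. The median fitted ratio was 2.05 for glove counts and 0.74 for no-glove counts, in line with reading (a).

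**The case against.** The strongest reply is that the working specification is already clear. The outcome sentence names gloves, the model sentence counts gloves, Section 5 gives glove pairs over razor blades, and the hypothesis concerns glove use. The items collected are gloves and razors, and no separate exposure count is described. On this view the blood-exposure wording is a labelling slip that a competent analyst would see through. The Aim 3 title and Section 9 (Limitations) only name the construct for which glove use is the measure.

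Much of this stands. The intended analysis can be recovered, and a title that names a construct is not an error in itself. The reversal also depends on exposure meaning no gloves, which the documents do not state. The description of the intervention arm in Section 5 supports that reading by treating PPE as the barrier against blood, but it is not a definition. The order of an example has no effect on a two-sided power calculation.

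The reply does not deal with the interpretation sentence, which tells the analyst how to report the correctly fitted model, and tells them wrongly. Nothing elsewhere corrects it. Other meanings of exposure do not rescue the text. If exposure meant any skin-cutting procedure, the numerator would nearly equal the denominator; if it meant something else, the primary numerator is undefined.

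**Conclusion.** The concern holds and should be corrected before analysis. That Section 7 contradicts itself on the primary outcome needs no assumption. That the stated reading reverses direction for every non-null effect rests on exposure being one minus glove use. The sizes in the table rest also on one common proportion per arm, without covariates; they are illustrations, not forecasts.

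The scope is limited. Sample size and the Table 1 powers do not change. If exposure is exactly one minus glove use, the t-test and Wilcoxon p-values do not change either, and only the sign flips. The negative binomial ratio and its p-value do depend on which count is modelled.

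**What to change.** The sponsor should confirm glove use as the primary outcome; the hypothesis, the measurement section and the model sentence all support it. Then:

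1. In Section 7, Aim 3, set the numerator to glove pairs (procedures with gloves) and the denominator to razor blades (procedures). Replace the blood-exposure wording in the definition, contrast, interpretation and sensitivity analyses.
2. State which team is in the numerator of the ratio and which direction is favourable, for example healer + HCW over HCW-only, with values above 1 favouring healer + HCW.
3. In Section 4, call the Table 1 delta a difference in glove use and restate the example with each value assigned to a named arm, consistent with the hypothesis. With the present values this puts the HCW-only arm at 0.2, below the preliminary mean of 0.39, so the sponsor should confirm or replace them.
4. If blood exposure is also of interest, define it and analyse it as a separately named outcome.

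These are wording changes to the protocol and SAP. Data collection, sample size and power stay as they are. No position is taken here on the model form or its covariates.

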Aim 2: We will rate training fidelity via two constructs: (1) content and (2) coverage^{41,42} during the week-long training session and community-based outreach sessions (Appendix 2). Understanding the fidelity of training delivery is essential to interpreting the effect of the intervention on PPE behavior change. If HCW + healer teams can deliver training with greater or equal fidelity than HCWs alone, PPE training can be more quickly scaled up nationwide (given the large number of healers) and conducted at lower cost (healers charge considerably less per hour than HCWs). We believe that the healer + HCW teams may have more motivation to deliver the program with fidelity during community-based sessions than the team of HCWs alone because of healers' desire to protect their peers living in their own community. Three HCWs who volunteer to work on this project will be randomly assigned to the intervention team (along with the healers), with six volunteer HCWs assigned to the control arm.

Aim 3: Healers will complete an interviewer-assisted survey immediately post training (Appendix 3) using the Consolidated Framework for Implementation Research framework⁴³ (compatibility of PPE with current behavior, peer pressure to use PPE, perception of the inclusiveness of the training process, cost) and individual characteristics from the situated-IMB model (Figure 3)^{44,45}. During the six months of the trial, healers in each arm will record data on our primary outcome: the proportion of injections conducted using PPE in two ways.

(1) Collect used sharps and PPE. Healers will be given containers to place all used gloves and razors/sharps to both ensure healer safety and allow us to count materials used (healers use gloves and a single razor once per patient and subsequently throw them into latrines or trash piles). We will use the *number of glove pairs as the numerator* (number of times they used gloves during procedures) and the *number of razor blades as the denominator* (number of injections given). While some may be concerned with social desirability bias, healers have been told for years to use gloves and were very open with us about their non-use. Healers have no reason to

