Aim 2: Analysis plan for content: A numeric scale will be used to assess the fidelity of the delivery of *each* topic in the training session. Topics include: (1) Delivered information about the definition of PPE, (2) Provided information about when to use PPE, (3) Provided information about what types of PPE to use in different circumstances, (4) Provided information about the appropriate fit of PPE, (5) Provided do's and don'ts of glove use, (6) Provided information about don PPE, (7) Provided information about how and where to remove PPE, (8) Provided information about how to safely store used PPE, (9) Provided information about hand hygiene, (10) Provided instruction and feedback during PPE practice session. Each of the ten training items will be scored (each with a score of 0-10; 10 represents the greatest fidelity to the training guide, 0 not covering the material at all) for a total of 100 points. The summation of all scores across topics will be used to measure fidelity to content for that training session. Each participant will participate in three training sessions. The mean difference between the two interventions in the total fidelity scores will be estimated using mixed effects linear regression models with 95% confidence intervals (CIs). These models will include random effects for the participant (to account for correlation across multiple sessions) and the trainer (to account for one trainer instructing multiple participants) and a 95% CI will be constructed. The outcome will be transformed as necessary to meet modeling assumptions. Covariates will include patient volume, sex, and baseline age. Any missing data will be imputed using chained equations with 20 imputation replications. Based on prior experience working with healers, we anticipate very low rates of loss to follow-up (LTFU). Healers who are LTFU will be censored at the time of their last recorded data collection, and inverse-probability of censoring weights based on healer characteristics randomization will be used, if necessary, to account for differences between healers who are LTFU and those who remain in the study.

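### The Aim 3 models leave out patient volume, a randomisation stratum that both Aim 2 models adjust for, and no reason is given (minor; a free improvement)

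*Combined protocol and SAP*

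**What the plan says.** **Design.** Section 4, Randomization strategy: "we will stratify based on healer sex and the number of patients seen in a given month". The count is split at the estimated median, which gives four strata, and "equal numbers of healers in each strata will be randomized to the two intervention arms".

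**Aim 2 models.** In section 7, Data Analysis, the content model and the coverage model each carry the same list: "Covariates will include patient volume, sex, and baseline age". The coverage model is a Poisson regression that also has an offset: "with the number of planned sessions (in most cases 3) as an offset".

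**Aim 3 models.** The primary model is a negative binomial regression of the number of times gloves were used, with the number of procedures (razor blades) as offset. Besides arm, "we will include healer sex and baseline age as covariates in our model". Of the choice of model the plan says that "it properly accounts for heterogeneity between healers in the number of procedures performed". The secondary outcome is to be analysed in the same way with a different count as outcome, so it takes the same covariates. No passage explains why volume appears in Aim 2 but not in Aim 3.

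**The concern.** Section 4 says that stratification is there to keep the arms from differing substantially, so volume was judged important enough to balance. The Aim 3 analysis then keeps one stratifier (sex) and drops the other. Section 4 also says that the sample size rests mainly on Aim 3.

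When a balanced stratifier predicts the outcome and is left out of a linear model, its variance stays in the residual. The reported standard error is then somewhat too wide, and a little power is given up. There is also a procedural cost. If volume is added later to match Aim 2, after outcome data have been seen, the change will look post hoc. Both matters are avoidable, because the stratum is recorded before randomisation.

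**Working it through.** **1. The plan's own figure.** Inputs from section 4: 61 healers per arm, SD 0.39, difference 0.20, alpha 0.05 (taken as two-sided, which reproduces Table 1).

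- SE = 0.39 × √(2/61) = 0.0706
- Noncentrality = 0.20 / 0.0706 = 2.832
- Power of the two-sample t-test (noncentral t, 120 df) = 80.22%, as in Table 1.

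**2. Does the offset already cover volume?** The offset enters as log(procedures) with its coefficient fixed at 1. That turns a count of glove uses into a proportion of procedures. It contains no term that lets this proportion differ between high- and low-volume healers. It also counts razor blades used during follow-up, whereas the stratum uses patients seen in the month before randomisation. The plan itself does not treat an offset as a reason to drop volume: the Aim 2 coverage model has both.

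**3. Linear approximation of what is at stake.** Let R² be the share of outcome variance that high/low volume explains beyond sex and age. The documents give no value, so a range is assumed. Healers are taken as independent, sex and age are in both models, and volume is balanced by design.

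- True SE in both models = 0.0706 × √(1 − R²)
- SE reported without volume = 0.0706 (118 df); with volume it equals the true SE (117 df)
- High-low gap in mean glove use implied by R² = 2 × 0.39 × √R²

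| Assumed R² | Implied gap | Power without volume | Power with volume | Gain (points) |
|---|---|---|---|---|
| 0 | 0 | 80.21% | 80.20% | −0.01 |
| 1% | 0.08 | 80.32% | 80.59% | 0.3 |
| 2% | 0.11 | 80.44% | 80.99% | 0.5 |
| 5% | 0.17 | 80.81% | 82.17% | 1.4 |

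An R² of 10% would give 81.44% against 84.15%, but it needs a gap of 0.25 between volume groups, larger than the 0.20 that the trial is sized to detect between arms.

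**4. The planned model.** The linear figures need not carry over to a negative binomial model with a log link. An illustrative simulation used 122 healers allocated 1:1 within strata, beta-distributed glove use around 0.39, an arm difference of 0.20, procedure counts averaging about 15 (low volume) and 40 (high volume), and 250 trials per setting. All distributional choices are assumptions. Each cell shows without → with volume.

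| Volume gap | Rejection, difference 0.20 | Mean log ratio | Empirical SD of estimate | Median model SE | Rejection under the null |
|---|---|---|---|---|---|
| 0 | 42.4 → 45.6% | 0.555 → 0.563 | 0.228 → 0.232 | 0.295 → 0.296 | 0.4 → 0.4% |
| 0.1 | 37.2 → 43.2% | 0.528 → 0.552 | 0.211 → 0.225 | 0.288 → 0.290 | 0.8 → 0.8% |
| 0.2 | 47.6 → 58.4% | 0.548 → 0.606 | 0.224 → 0.265 | 0.281 → 0.280 | 0.8 → 1.2% |

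The Monte Carlo error of a single rejection rate is about √(0.45 × 0.55 / 250) = 3 points. The absolute rejection rates reflect the assumed distributions and are not an estimate of the trial's power. Under the null, the mean log ratio stayed between 0.002 and 0.015 with or without volume. With volume in the model, rejection under the alternative was higher, partly because the estimated coefficient itself moved. The empirical spread of the estimate did not fall. At a gap of 0.3, beyond the plausible range, the same pattern was stronger (rejection 45.6 → 63.2%, empirical SD 0.192 → 0.277).

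No calculation was made for the secondary outcome.

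**The case against.** The strongest reply is that nothing in the trial turns on this. Balance on volume is secured by the randomisation, so leaving it out does not confound the comparison. The sample size calculation used a t-test with no covariates, so its 80.22% never depended on adjusting for volume. Every non-zero gain in the linear table rests on an R² that the documents do not supply. The model in question is also negative binomial, where simulation showed no fall in the spread of the estimate and a null rejection rate already well below 5% either way. All of this stands, and it limits the point to an unexplained inconsistency with a free remedy.

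One could also say that the procedures offset already deals with busy and less busy healers. This part does not stand, for the reasons in step 2 of the working.

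A reader might infer something stronger: that the Aim 3 comparison is biased, that the trial is underpowered, or that adjusting for volume is sure to tighten the interval. The documents support none of these. Allocation is equal within strata, the stated power reproduces without any adjustment, and no association between volume and glove use is reported.

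**Conclusion.** The inconsistency is plain on the text. Volume is a randomisation stratum and a covariate in both Aim 2 models, yet it is absent from the Aim 3 primary model and, by inheritance, from the secondary one, without explanation. It is minor. The arm comparison is not materially biased and the stated power is not undercut.

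The possible gain is about 0.3 to 1.4 points of power for an assumed R² of 1 to 5%, against a cost of about 0.01 point if volume is unrelated to glove use. These figures are hypothetical and hold only in a linear approximation with independent healers. For the planned negative binomial model, the simulations support saying that adding volume left the chance of detecting the effect similar or higher under the assumptions used. They do not support a claim of better precision, nor a claim that the linear over-wide standard error describes that model. For the secondary model the case rests on consistency alone.

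**What to change.** Before outcome data are seen, add the high/low patient-volume stratum, in the form used at randomisation, to the covariates of the Aim 3 primary model alongside sex and baseline age. For consistency, do the same in the secondary model. If volume is left out on purpose, one sentence giving the reason is enough. The t-test and Wilcoxon sensitivity analyses can stay as they are.

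The cost is a change of wording in section 7 and one degree of freedom. The variable is already collected for randomisation, and neither the sample size nor the trial procedures change.

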Our intervention arm will receive the same training and educational outreach as the control arm, but with training and outreach conducted by a clinical team that includes healers who adopted and use PPE on their own (early adopters).³⁷⁻⁴⁰ Early adopters are people who identify a new behavior as innovative (i.e. use of latex gloves) and adopt this behavior before the majority of their colleagues. Used primarily in the Diffusion of Innovation Theory⁵² to explain adoption of new behaviors, we hypothesize that the strategy of engaging early adopting healers as trainers in collaboration with HCWs will increase peer pressure, perceived tension for change, participant self-efficacy, and acceptability of PPE use among healers who do not use any barrier to blood exposure. Early adopters can achieve this by highlighting relative advantages, compatibility with their role of a traditional healer and leader in the community, simplicity, and ease of trialability of using gloves with patients.⁵²

Participants will receive a baseline and end line (7 months post- training) HIV test (to detect any seroconversion events and to determine if those living with HIV are as motivated to use PPE as those who are HIV-negative). Participants will also complete baseline and end line surveys to assess their knowledge, motivation, and behavioral skills to determine the impact of training on the healer. Once a month, a study assistant will visit each healer to collect all used sharps and PPE; three times during the study the study assistant will also conduct observations of healers using PPE to determine if they are using it correctly post-training.

Healers and healer care workers who are selected, consent and contribute to the training of healers will be reimbursed for their transportation to the training venue and provided with a small token of appreciation (a voucher to a local store for R150) at the conclusion of the workshops.

6. Study Location

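### The Aim 3 primary model leaves out the healer's own pre-training glove use; adding it to the baseline survey and the model is a cheap gain in precision and balance, of uncertain size

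*Combined protocol and SAP*

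**What the plan says.** **Primary model** (Section 7, Data Analysis, Aim 3). Negative binomial regression of the number of times gloves were used, with the number of procedures (razor blades) as offset. Beside study arm, "we will include healer sex and baseline age as covariates in our model". The sensitivity analyses are a two-sample t-test and, as needed, a Wilcoxon rank sum test, with no covariates mentioned.

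**Stratification** (Section 4, Randomization strategy). Four strata, formed by healer sex and by high or low patient volume, split at the "estimated median number of patients seen in the past month". Prior glove use is not a factor.

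**Sample size** (Section 4, Calculation of Sample Size & Sampling Strategy, Aim 3). In the 2019 Agincourt data, "the median proportion of glove use during vaccinations was 0.44, mean 0.39, and standard deviation (SD) 0.39". The plan then says: "Our sample size is calculated based on a two-sample t-test and incorporates these preliminary data". The target is "a difference of 0.2 in the proportion glove use between the HCW-only and the healer + HCW teams", with 61 healers per arm. Table 1 gives 80.22% power for that case.

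**Baseline data** (Section 5, Study Procedures, Aims 2 & 3). "Participants will also complete baseline and end line surveys to assess their knowledge, motivation, and behavioral skills". The items shown in Appendix 3 do not ask how often gloves are used. A glove-use question for healers appears only in the Aim 1 interview guide (Appendix 1). The primary outcome is collected over the six months of the trial (Section 5, Measurement of Results), and no pre-training count of gloves and blades is described.

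**The concern.** Healers enter the trial with very different habits. The preliminary variance is 0.39² / (0.39 × 0.61) = 64% of the largest possible for a 0 to 1 variable with mean 0.39. A healer's earlier glove use is a natural candidate to predict later use, yet the model adjusts only for sex and age.

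Two things are at stake. One is power: 61 per arm is the smallest size that reaches 80% for a 0.20 difference, and it is not inflated for loss to follow-up. The other is balance. The stated purpose of stratifying is to keep the arms from differing substantially despite randomization, but sex and patient volume do not secure balance on prior glove use. Without a baseline measure, an imbalance could be neither seen nor adjusted for.

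**Working it through.** **Inputs.** From Section 4: SD 0.39, difference 0.20, n = 61 per arm, α = 0.05. The text does not say whether the test is two-sided; a two-sided test reproduces Table 1. The correlation r between baseline and follow-up glove use is not in the documents and is varied as an assumption.

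**Step 1: the plan's own figure.** Two-sided two-sample t-test, df = 2 × 61 − 2 = 120.
- Standard error of the difference = 0.39 × √(2/61) = 0.0706.
- Noncentrality = 0.20 / 0.0706 = 2.83.
- Power from the noncentral t = 80.22%, as stated. All nine rows of Table 1 match to two decimals, and 60 per arm gives 79.56%.

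**Step 2: baseline covariate, t-test (ANCOVA) approximation.** Residual SD = 0.39 × √(1 − r²), df = 119.

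| r (assumed) | Residual SD | Power, 61 per arm | n per arm for 80% | Detectable difference at 80% |
|---|---|---|---|---|
| 0 | 0.390 | 80.2% | 61 | 0.200 |
| 0.2 | 0.382 | 81.8% | 59 | 0.195 |
| 0.3 | 0.372 | 83.8% | 56 | 0.190 |
| 0.5 | 0.338 | 90.0% | 46 | 0.173 |
| 0.7 | 0.279 | 97.6% | 32 | 0.142 |

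If r were zero, the cost would be one degree of freedom, which leaves power at 80.2%.

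**Step 3: the planned model.** The primary analysis is a count model, so Step 2 is only a guide. A small simulation of a negative binomial model with offset used 400 trials per setting, 61 per arm, assumed means 0.50 and 0.35, assumed SD 0.30, about 31 procedures per healer, fixed dispersion and robust standard errors. Power without and with the covariate was:
- latent correlation 0.3: 74.5% and 74.5%;
- 0.5: 74.8% and 79.8%;
- 0.7: 73.5% and 90.8%.

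The Monte Carlo standard error of each figure is about √(0.75 × 0.25 / 400) = 2.2 points. A second simulation, also with assumed inputs but with a noisy one-month baseline, gave gains of under 1, about 3 and about 9 points at the same correlations.

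**Step 4: chance imbalance.** If baseline glove use also has SD 0.39, its arm difference has standard error 0.0706. By the normal approximation, an imbalance of at least 0.10 in either direction has probability of about 16% (z = 0.10 / 0.0706 = 1.42). With equal SDs and r = 0.5, an imbalance of 0.10 moves the unadjusted estimate by 0.5 × 0.10 = 0.05, a quarter of the 0.20 target.

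**Step 5: loss to follow-up, as an illustration.** With 55 per arm (about 10% loss, an assumed rate), the same approximation gives 76.0% unadjusted, 79.8% at r = 0.3 and 86.8% at r = 0.5.

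**The case against.** The strongest reply is that nothing here is wrong. The plan claims an unadjusted 80.22% and gets it. Leaving out an optional prognostic covariate in a randomized trial does not bias the comparison, and it contradicts nothing in the documents. That stands, and it makes this an improvement rather than a correction.

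A second reply is that r may be low. Both arms receive training and outreach meant to change glove use. The baseline would be recalled self-report over a short period, set against six months of container counts. The SD of 0.39 includes sampling noise from each healer's number of procedures, so it does not show that individual use is stable. This also stands. At r = 0.2 even the t-test approximation gains only 1.6 points, and the count-model simulations show little or nothing at 0.3.

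A third reply is that the item may already be asked. The baseline survey is said to cover behavioral skills, and Appendix 3 Part A is headed as examples. The documents support saying only that the item is not specified and not used, not that it is certainly absent.

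These replies limit the size of the benefit. They do not remove the case for a covariate that costs one degree of freedom and lets the investigators check balance on a likely predictor. The Section 5 remark that healers spoke openly about not using gloves also suggests that the question can be asked.

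**Conclusion.** The point holds as a cheap improvement. The Aim 3 analysis forgoes precision and protection against chance imbalance by not measuring and adjusting for pre-training glove use.

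A reader might infer that the trial is underpowered or its primary analysis invalid because of this omission. The documents do not support that: the stated power does not depend on adjustment, and it reproduces. A reader might also take 90% or 98% as the power the trial would have. That does not follow either, because those figures assume r = 0.5 or 0.7 and a t-test, while the documents report no r and plan a negative binomial model. Under that model the likely gain is little or none at r of 0.3 or below, a few points at 0.5, and roughly 9 to 17 points at 0.7, all under assumed inputs.

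**What to change.** 1. **Collect it before training.** In the existing baseline survey, if not already asked, record the number of injections in a stated recall period (for example the past month, as for the patient count) and how many were done with gloves. Changing the model text alone is not enough.
2. **State a rule for healers with no injections in that period**, since their proportion is undefined. Eligibility requires that a healer conducts vaccinations, not recent ones.
3. **Prespecify the baseline glove-use proportion as a covariate** in the negative binomial model. First reconcile the Aim 3 text in Section 7, which defines the numerator as procedures with blood exposure but models the number of times gloves were used. The covariate should be on the same glove-use scale as the outcome.
4. **Add an ANCOVA beside the planned two-sample t-test.** Keep the t-test, because it matches the power calculation.
5. **Report the observed baseline-to-follow-up correlation**, which would help size the larger trial that the plan foresees.

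The cost is two survey questions, slightly longer interviews and one model term, with no new visit. The drawback is that the baseline is recalled self-report. If training has already taken place without the question, an uncontaminated baseline can no longer be collected.
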